1.2 Verdiperstat Rationale

Oxidative stress

Based on extensive supportive evidence from human ALS and animal models, oxidative stress is thought to promote neurodegeneration in ALS and other disorders [4]. MPO catalyzes generation cytotoxic oxidizing and nitrosylating compounds, e.g., hypochlorous acid and peroxynitrite [5] [6] which are strongly implicated in the pathophysiology of ALS. This is because biological macromolecules undergo oxidative damage by reactive oxygen and nitrogen species (ROS/RNS), which leads to organelle dysfunction and neuronal death. Free radical scavengers and other antioxidants are obvious treatment approaches but have had disappointing effects in clinical trials. Advances in ROS/RNS biology explain the failure of such antioxidants and suggest more mechanistic strategies for reducing oxidative stress. ROS/RNS are not merely toxic metabolic waste products. Rather, they are part of complex cellular signaling networks that include ROS/RNS producing enzymes (MPO, NADPH oxidase [NOX], xanthine oxidase), ROS targets (NF- κ B mediated inflammatory pathways, inflammasomes), and ROS-metabolizing enzymes (SOD and NRF2-regulated antioxidant pathways). Deregulation of ROS/RNS pathways contributes to other known neurodegenerative disease mechanisms, i.e., microglial activation and neuroinflammation. Thus, it may be advantageous to inhibit ROS/RNS producing enzymes, such as MPO, thereby reducing oxidative stress and inflammation in a physiologic manner. The general relevance of this strategy is supported by preliminary data that suggest inhibiting NOX reduces microglial activation and may have other benefits in an ALS model [7].

Neuroinflammation

Based on extensive supportive evidence from human ALS and animal models, neuroinflammation is also thought to be an important mediator of neurodegeneration in ALS and other disorders [8], [9]. Microglia, the primary innate immune cells of the brain, are central players that drive neuroinflammation. In disease, resting microglia are activated or transformed into a pathological “M1” phenotype that is characterized by secretion of pro-inflammatory cytokines and ROS/RNS as well as an amoeboid morphology and phagocytic properties similar to peripheral macrophages. Modulating microglial activation is a promising and common therapeutic strategy for neurodegenerative diseases, including ALS. However, it is unclear how to determine the optimal molecular target for intervention in this dynamic, in vivo process from studies in disease models.

Positron emission tomography (PET) imaging of translocator protein (TSPO) is a state-of-the-art method for assessing pathological neuroinflammation in human disease states. Because TSPO is highly expressed in activated microglia, signal from TSPO-specific radioligands, such as [11 C]-PBR28, is interpreted as a measure of microglial activation. [11 C]-PBR28 PET signal is dynamic, responsive to treatment, and potentially predictive of benefit on clinical outcome measures. Thus, [11 C]-PBR28 PET is a valuable pharmacodynamic biomarker for anti-inflammatory therapies that can demonstrate central target engagement and provide proof of mechanism of action in human neurodegenerative disorders [10]. Cross-sectional and longitudinal [11 C]-PBR28 PET studies in participants with ALS show that [11 C]-PBR28 signal is increased in ALS but

stable over at least 6 months of disease progression. Corresponding sample size and power calculations suggest [¹¹C]-PBR28 PET is a sensitive biomarker allowing for efficient signal detection in smaller, early phase studies. Several such studies are ongoing to assess investigational treatments in ALS, however none of these treatments has yet demonstrated the ability to decrease [¹¹C]-PBR28 uptake. By contrast, MPO inhibition is the only approach that has demonstrated the ability to decrease [¹¹C]-PBR28 uptake in human neurodegenerative disease, highlighting the therapeutic relevance of this target for ALS.

Additional

MPO may also play a role in increasingly recognized disease mechanisms mediated by peripheral myeloid cells, including those that migrate into the brain as well as those that remain in the periphery [8], suggesting relevance of MPO as a therapeutic target at both sites. For example, circulating immune cell numbers (particularly neutrophils) appear to correlate with ALS disease progression measured by ALSFRS-R. And, MPO⁺ neutrophils seem to contribute to distal motor axon and muscular pathology in human ALS autopsy tissue and in an ALS animal model.

1.2.1 Dosage Selection and Justification

The dosage of verdiperstat selected for evaluation in this study is 600 mg BID. This dosage was selected based on cumulative experience, including nonclinical toxicology and safety/tolerability, pharmacokinetic, pharmacodynamic, and preliminary efficacy data from phase 1 and phase 2 studies.

Nonclinical toxicology: The program for verdiperstat is comprehensive and supports oral administration in the clinic for chronic treatment. The following studies were included in the toxicology program: single and repeat-dose toxicity in rats and dogs, genotoxicity, reproductive toxicity, phototoxicity, and safety pharmacology. The verdiperstat 600 mg BID dosage is anticipated to produce pharmacokinetic exposures below limits set based on nonclinical toxicology data.

Clinical studies: As of January 2021, approximately 490 subjects have received verdiperstat in completed and ongoing studies. In the phase 1 studies (5 completed studies) in healthy subjects, treatment with multiple dosages of up to 900 mg BID was generally safe and well tolerated. In the completed phase 2 studies in participants with Parkinson's disease and Multiple System Atrophy (MSA), treatment at dosages of up to 600 mg BID for 8-12 weeks was generally safe and well tolerated. In the phase 2 studies, the 600 mg BID dosage decreased MPO activity in plasma, providing evidence of peripheral target engagement; reduced TSPO binding on brain PET imaging, providing evidence of central target engagement and proof of mechanism (decreased microglial activation/neuroinflammation); and demonstrated favorable, dose-dependent trends on clinical efficacy measures at 12 weeks in subjects with MSA.

A phase 3 study in patients with MSA is ongoing and currently is still blinded. In this study, approximately 336 subjects have received verdiperstat or placebo. Subjects are randomized 1:1

to receive verdiperstat or placebo, 600 mg BID, for 48 weeks with the option to continue in the study for an additional 48 weeks of open-label treatment with verdiperstat. Please refer to the Investigator's Brochure [3] for additional information.

2 STUDY OBJECTIVES AND ENDPOINTS

Primary Efficacy Objective:

To evaluate the efficacy of verdiperstat as compared to placebo on ALS disease progression.

Secondary Efficacy Objective:

- To test the effect of verdiperstat on selected secondary measures of disease progression, including survival.

Safety Objective:

- To evaluate the safety of verdiperstat for ALS.

Exploratory Efficacy Objective:

- To test the effect of verdiperstat on selected biomarkers and endpoints.
- To explore verdiperstat pharmacokinetics (PK) and pharmacodynamic (PD) effects.

Primary Efficacy Endpoint:

Change in disease severity as measured by the ALS Functional Rating Scale-Revised (ALSFRS-R) total score using a Bayesian repeated measures model that accounts for loss to follow-up due to mortality.

Secondary Efficacy Endpoints:

- Change in respiratory function as assessed by slow vital capacity (SVC).
- Change in muscle strength as measured isometrically using hand-held dynamometry (HHD) and grip strength.
- Survival.

Safety Endpoints:

- Treatment-emergent adverse and serious adverse events.
- Changes in laboratory values and treatment-emergent and clinically significant laboratory abnormalities.
- Changes in ECG parameters and treatment-emergent and clinically significant ECG abnormalities.
- Treatment-emergent suicidal ideation and suicidal behavior.

Exploratory Efficacy Endpoints:

[figure not shown]
- Changes in quantitative voice characteristics.
- Changes in biofluid biomarkers of neurodegeneration.

- Changes in patient reported outcomes.
- Changes in verdiperstat PK and PD biomarkers.
- Change in respiratory function as assessed by home spirometry.

3 RSA DESIGN

This study is a multicenter, randomized, double-blind, 2-arm placebo-controlled parallel-group study designed to evaluate the efficacy and safety of verdiperstat in a population of participants with ALS. The study is planned to consist of a Screening phase lasting a maximum of approximately 6 weeks (42 days) and a randomized double-blind treatment phase of approximately 24 weeks (see Figure 1). It is anticipated that the Randomization phase will include a dose titration period of approximately 2 weeks followed by a full dosage period of approximately 22 weeks. Participants completing 24 weeks of treatment with verdiperstat or placebo will be eligible to continue to an Open-label Extension Phase (OLE) which will include an additional 52 weeks of dosing. Approximately 160 participants in total are planned to be randomized in a 3:1 ratio to receive either verdiperstat 600 mg BID, or matching placebo BID. The assessments for each visit are outlined in the Schedule of Activities (SoA).

Figure 1. Regimen Specific Appendix Schematic

3.1 Scientific Rationale for RSA Design

This RSA is designed to correspond with the design of the Master Protocol and the goals of that study.

3.2 End of Participation Definition

A participant is considered to have ended his or her participation in the placebo-controlled period of the Regimen if they:

- Complete planned placebo-controlled period visits, as described in the SOA, including participants on or off study drug
- Early terminate from the study and complete the Early Termination Visit and Follow-Up Phone call as described in Section 6.1.11
- Withdraw consent to continue participation in the study, or are lost to follow-up

If a participant initiates open-label study drug in the OLE period, he or she is considered to have completed his or her participation in the OLE period of the Regimen if they choose to discontinue participation or if all planned OLE period visits, including the last visit or the last scheduled procedure shown in the SOA, have been completed.

3.3 End of Regimen Definition

The end of the placebo-controlled period in a Regimen occurs when all randomized participants have completed their participation in the placebo-controlled period as defined in section 3.2.

The end of the OLE period in a Regimen occurs when all participants who initiated open-label study drug in the OLE period have completed their participation in the OLE period as defined in Section 3.2.

4 RSA ENROLLMENT

4.1 Number of Study Participants

Approximately 160 participants will be randomized into this Regimen.

4.2 Additional RSA Inclusion and Exclusion Criteria

To be randomized to an RSA, participants must meet the Master Protocol eligibility criteria. In addition, participants meeting all the following inclusion and exclusion criteria will be allowed to enroll in this Regimen.

4.2.1 RSA Inclusion Criteria

There are no additional RSA Inclusion Criteria from those described in the Master Protocol.

4.2.2 RSA Exclusion Criteria

- Participants who are taking strong inhibitors of CYP1A2 (i.e., ciprofloxacin, enoxacin, fluvoxamine, zafirlukast) for chronic/long-term use defined as more than two weeks.
- Participants who are taking strong inhibitors of CYP3A4 (i.e., conivaptan, itraconazole, ketoconazole, posaconazole, troleandomycin, voriconazole, clarithromycin, diltiazem, idelalisib, nefazodone, and certain antiviral agents [cobicistat, danoprevir, ritonavir, elvitegravir, indinavir, lopinavir, paritaprevir, ombitasavir, dasabuvir, saquinavir, tipranavir, nelfinavir]) for chronic/long-term use defined as more than two weeks. Note: Topical antifungal use is not exclusionary. Participants should not consume large quantities of grapefruit juice (more than 8oz per day) on a regular basis.

There are RSA-specific requirements that apply to Master Protocol exclusion criteria #6. For further details of contraceptive requirements for this RSA, please refer to Section 5.8.2.

*Guidance regarding CYP1A2 and CYP3A4 has been updated in Protocol Section 5.8 Drug-Drug Interactions and Prohibited Medications, however this exclusion criteria has **not** been modified as all participants have been enrolled.*

4.3 Treatment Assignment Procedures

Each participant who meets all eligibility criteria for the RSA will be randomized to receive either verdiperstat or matching placebo for approximately 24 weeks of treatment. Participants who complete the 24-week blinded Treatment Period will be eligible to continue treatment with open-label verdiperstat for an additional 52 weeks.

5 INVESTIGATIONAL PRODUCT

The Investigational Product (IP) should be stored in a secure area according to local regulations. It is the responsibility of the Site Investigator (SI) to ensure that the IP is only dispensed to study participants. The IP must be dispensed only from official study sites by authorized personnel according to local regulations.

In this protocol, the IP is verdiperstat 300 mg extended release (ER) tablets and matching placebo tablets.

5.1 Investigational Product Manufacturer

Biohaven Pharmaceuticals, Inc. is the manufacturer of verdiperstat.

5.2 Labeling, Packaging, and Resupply

5.2.1 Labeling

Container(s) of investigational product will bear a label containing (at a minimum) the name of the study drug, lot and/or batch number and appropriate storage conditions (15°-25°C [59°-77°F] [see USP controlled room temperature] in a tightly closed container, protected from light).

The drug product is presented as verdiperstat Extended Release (ER) Tablets that are reddish-beige, film coated and oval (300 mg strength). The tablets each consist of 300 mg of verdiperstat drug substance as free base, and generally recognized as safe (GRAS) excipients for oral dosage forms including hydroxypropyl methyl cellulose, microcrystalline cellulose, hydroxypropyl cellulose, sodium stearyl fumarate and orange color. Matching placebo tablets contain microcrystalline cellulose and sodium stearyl fumarate and are film-coated with OPADRY® (mixture of hypromellose, polyethylene glycol and titanium dioxide) and iron oxide to give reddish-beige color. The tablets are packed in high-density polyethylene (HDPE) bottles. The bottles are induction sealed and closed with child resistant polypropylene (PP) screw caps.

All investigational products should be kept in a secure area with limited access under appropriate storage conditions: 15°-25°C (59°-77°F) (see USP controlled room temperature) in a tightly closed container, protected from light.

Excursions outside this storage temperature range should be reported as per the Pharmacy Manual Instructions.

5.2.2 Acquisition and Preparation

Initially, after informed consent is obtained at the Screening Visit, the SI or designee will enter the participant into the study and obtain a participant number assignment. After completion of Screening evaluations, all eligible participants will be randomized, in a 3:1 ratio to receive either verdiperstat (600 mg BID) or matching placebo, using an EDC.

5.2.3 Drug Returns and Destruction

At each in person visit the steps outlined in Manual of Procedures must be followed for study drug accountability and compliance, as well as study drug return and destruction.

Prior to study drug destruction, all used and unused IP requires a second accountability verification to be completed by a different study team member, and both verifications should be documented on the study destruction logs. No study drug may be destroyed on-site until written approval is provided by the study monitoring team. Sites should follow their local drug destruction policies.

5.3 Study Medication/Intervention, Administration and Duration, and Titration

All participants will be randomized to receive verdiperstat 600 mg BID or matching placebo BID. Participants should take the study drug twice a day; dosing in the morning and evening approximately 12 hours apart.

The tablets should be swallowed whole with a drink of water (or other liquid) or swallowed with substances of other consistencies as appropriate (e.g., apple sauce). The tablets should not be split, chewed, or crushed.

Study medication can be taken without regard to meals.

5.3.1 Administration and Duration

Day 1/first dose:

Participants should be administered the Day 1/first dose of study medication (300 mg QD or matching placebo QD) while in the office/clinic on the day of the Regimen-Specific Baseline visit after all visit assessments are complete. Participants should stay at the office/clinic for monitoring for approximately 30 minutes post-dose.

Dose titration period:

From the beginning to the end of Week 1 participants should ingest either 300 mg QD of verdiperstat or matching placebo QD. From the beginning to the end of Week 2, participants should ingest either 300 mg BID of verdiperstat or matching placebo BID.

At the end of Week 2, an assessment of compliance and tolerance to this dose titration schedule will be conducted. The assessment will be conducted by phone. If tolerability issues are experienced with 300 mg QD or 300 mg BID dosing, the titration schedule may be modified (see 5.3.2).

Full dose period:

Starting with the beginning of Week 3 and throughout the remainder of the study, participants should ingest either 600 mg BID of verdiperstat or matching placebo BID.

At the Weeks 4, 8, 16, and 24 study visits, the morning dose of study medication should be held on the day of the study visit and administered in the clinic/office during the study visit, to collect one pre-dose (trough) PK and PD blood sample (see Section 8).

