² The last visit for the open-label extension will be at Week 52. Participants who withdraw consent or terminate early (prior to Week 52) from the study will be asked to be seen for an in-person Early Termination Visit and should have the same procedures as the Week 52 visit.

³ Participants who continue into the OLE and then early terminate will be asked to complete an Early Termination Visit and Follow-Up Safety Call as described in the body of this RSA.

⁴ Participants will have a Follow-up Safety Call approximately 28 days after the last dose of study drug. At this call, information on clinical status should be collected.

⁵ Vital signs include weight, systolic and diastolic pressure, respiratory rate, heart rate and temperature.

⁶ Clinical safety labs include hematology (CBC with differential), complete chemistry panel, liver function tests, thyroid function (TSH) and urinalysis. Serum pregnancy testing will occur in women of child-bearing potential at the Master Protocol Screening Visit and as necessary during the study. Pregnancy testing is only repeated as applicable if there is a concern for pregnancy.

⁷ Myeloperoxidase protein and activity, and plasma concentrations of verdiperstat will be measured. For each sample, the time of the last verdiperstat dose prior to sample collection, time of the last meal prior to sampling, and time of the PD/PK sample collection should be reported on the CRF.

⁸ Administer first dose of investigational product (IP) only after Week 24 procedures are completed. Participants should take the first dose of IP while in the office/clinic on the day of the Week 24 visit and stay at the clinic for approximately 30 minutes post-dose for observation.

⁹ From start to end of Week 1, participants will ingest 300 mg QD of verdiperstat QD. From start to end of Week 2, participants will ingest 300 mg BID of verdiperstat BID. Starting with Week 3 and continuing to Week 52, participants will ingest 600 mg BID of verdiperstat BID.

¹⁰ Participants should be instructed to skip the morning dose of study drug on the day of the study visit – at OLE Weeks 16, 28 and 52. Study drug should not be taken until after study visit procedures are complete.

¹¹ Visit may be conducted via phone or telemedicine with remote services instead of in-person if this is needed to protect the safety of the participant due to a pandemic.

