6.1.9 Week 24 Visit or Early Termination Visit

Participants should be instructed to skip the morning dose of study drug on the day of the study visit. Study drug should not be taken until after study visit procedures are complete.

The Week 24 Visit will take place in-person 168 ± 7 days after the Baseline Visit. The following procedures will be performed at either the Week 24 Visit or the Early Termination Visit for the regimen schedule:

- Home Spirometry
- ALSAQ-40
- CNS Bulbar Function Scale
- Collection of plasma samples for verdiperstat PD biomarkers (MPO protein and activity) and a plasma PK sample
- Voice Recording
- Uninstall Smartphone App
- Dispense IP (only if continuing in OLE)
- Remind participant to bring IP to the next visit

For participants rolling into the OLE, all participants should be instructed to follow the dose escalation scheme.

- After all Week 24 procedures are completed, administer a single 300 mg tablet of verdiperstat. Participants should stay at the clinic for approximately 30 minutes for observation.
- Dispense study drug to last for the next 4 weeks.
- Participants should be instructed:
 - To ingest 300 mg QD of BHV-3241 for the rest of Week 1.
 - To ingest 300 mg BID of BHV-3241 starting at the beginning of Week 2. Participants should take the study drug twice a day; dosing in the morning and evening approximately 12 hours apart.
 - If tolerability issues are experienced with 300 mg QD or 300 mg BID dosing, the titration schedule may be modified (see Section 5.3.2).
 - To ingest 600 mg BID of BHV-3241 starting at the beginning of Week 3 and through the remainder of the 52-week OLE. Participants should take the study drug twice a day; dosing in the morning and evening approximately 12 hours apart.

For participants NOT rolling into the OLE:

A Follow-up Safety Call should be scheduled approximately 28 days after last dose of study drug to collect clinical status information.

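### At Week 24, Sections 5.3.1 and 8.2 have the held blinded dose given in clinic, while Section 6.1.9 and the OLE schedule set one 300 mg open-label tablet for OLE entrants and no dose for the others

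*Protocol*

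**What the plan says.** Protocol Section 5.3.1 covers Week 24 in its paragraph on the full dose period. The placebo arm takes the corresponding placebo tablets; for the active arm the dose then in force is stated as "Starting with the beginning of Week 3 and throughout the remainder of the study, participants should ingest either 600 mg BID of verdiperstat". The sentence on sampling visits names Week 24 alongside Weeks 4, 8 and 16 and says that "the morning dose of study medication should be held on the day of the study visit and administered in the clinic/office during the study visit". Its stated purpose is a pre-dose trough sample. Section 8.2 gives the same hold-then-give instruction for the same four visits. Neither section makes an exception for Week 24 or for OLE entrants.

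Protocol Section 6.1.9, which governs the Week 24 visit, tells participants to omit the morning dose and take no study drug until procedures are finished. For those continuing into the OLE it then says "After all Week 24 procedures are completed, administer a single 300 mg tablet of verdiperstat", followed by the instruction "To ingest 300 mg QD of BHV-3241 for the rest of Week 1". Footnote 8 of the OLE schedule agrees: "Administer first dose of investigational product (IP) only after Week 24 procedures are completed", with that dose taken in clinic on the day of the Week 24 visit. Footnote 9 sets 300 mg once daily through OLE Week 1.

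For participants who do not continue, Section 6.1.9 lists only a safety call. Footnote 14 of the placebo-controlled schedule limits Week 24 dispensing to OLE entrants. The administer/dispense row of the SAP schedule (Section 2.9) has no Week 24 entry.

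**The concern.** Week 24 is both the last blinded visit and the first day of a new titration, so the dose given in clinic that day needs a single statement. Sections 5.3.1 and 8.2 point to the blinded dose then in force. Section 6.1.9 and the OLE footnotes point to a different product and amount. No passage says that the open-label tablet takes the place of the held dose, or that the held dose is dropped.

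What is at stake is dosing consistency and participant safety on that day. Sites may handle the same visit differently. If a site gives both, former active participants begin the OLE with more drug than the titration schedule sets, while former placebo participants do not. The observation period specified after the first OLE dose is about 30 minutes. For non-entrants, sites may differ on whether a last blinded dose is given at all.

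**Working it through.** There is no planned figure to reproduce. The check sets the passages side by side and then tallies the doses under each reading.

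**Inputs**
- Tablet strength: 300 mg (Protocol Section 5; SAP Section 2.7).
- Full dose: two tablets twice daily (SAP Section 2.7), so one morning dose is 2 × 300 = 600 mg, or two placebo tablets.
- Reduced dose permitted for tolerability: 300 mg twice daily (Protocol Section 5.3.2), so one morning dose is 300 mg.
- First OLE dose: one 300 mg tablet (Protocol Section 6.1.9).
- Schedule for that day: 300 mg once daily (OLE schedule footnote 9, with the Week 24 visit as OLE Day 0).

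**Instructions for the Week 24 visit**

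| Source | OLE entrants | Non-entrants |
|---|---|---|
| Protocol 5.3.1 and 8.2 | held blinded dose given in clinic | held blinded dose given in clinic |
| Protocol 6.1.9 | one 300 mg open-label tablet after procedures | no dose listed |
| OLE footnotes 8 and 9 | first OLE dose in clinic; 300 mg once daily in Week 1 | not applicable |
| Placebo-controlled schedule, footnote 14 | drug dispensed | drug not dispensed |
| SAP 2.9, administer/dispense row | no Week 24 entry | no Week 24 entry |

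**Does the line about omitting the morning dose settle it?** It appears in Section 6.1.9 and in schedule footnote 18. Sections 6.1.4, 6.1.5 and 6.1.7 carry the same line for Weeks 4, 8 and 16, where Section 5.3.1 has the dose given in clinic. At those visits it can only mean that the dose is not taken at home beforehand. Its presence at Week 24 therefore does not show that the dose is cancelled.

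**Verdiperstat received in clinic by an OLE entrant**

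| Former status | Open-label tablet only | Held dose also given |
|---|---|---|
| Active, full dose | 300 mg | 600 + 300 = 900 mg |
| Active, reduced to 300 mg twice daily | 300 mg | 300 + 300 = 600 mg |
| Placebo | 300 mg | 0 + 300 = 300 mg |

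Against the 300 mg scheduled for that day, the first two rows of the last column are 900/300 = 3 times and 600/300 = 2 times.

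**How many participants.** The RSA summary plans 120 active participants. That is a ceiling only. Section 6.2 admits to the OLE those who completed the blinded period on drug, and the documents give no OLE entry rate.

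**The case against.** The best reply is that Section 6.1.9 is the visit-specific text and reads naturally as one dose: omit the morning dose, finish the procedures, then give OLE entrants one tablet. On this view the Section 5.3.1 sentence exists only to secure a trough sample and was never meant as an order about OLE dosing. A site that added the blinded dose would breach the once-daily instruction in footnote 9. Much of this stands. Two doses is not the only reading, and 900 mg fits no single schedule. It does not remove the conflict, because Sections 5.3.1 and 8.2 name Week 24 and call for the dose to be given as well as held.

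For non-entrants, footnote 14 is a partial answer. It concerns dispensing, however, and does not say whether the held dose is given from supply already issued.

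A reader might infer three stronger points that the documents do not support.
- **That the protocol orders 900 mg.** It does not; the passages conflict, and giving both doses would itself break one of them.
- **That 900 mg is a known hazard.** Protocol Section 1.2.1 reports that multiple dosages up to 900 mg twice daily were generally safe and well tolerated in healthy subjects.
- **That adverse events around Week 24 can no longer be assigned.** SAP Section 6.6.1 ends the treatment-emergent interval no later than the date of the first OLE dose and has a rule for incomplete onset dates, so the analysis boundary is defined.

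The Master Protocol and Manual of Procedures were not available, so a clarification there cannot be excluded. The RSA passages would still disagree with one another.

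**Conclusion.** The Week 24 instructions in Sections 5.3.1 and 8.2 cannot be followed together with Section 6.1.9 and OLE footnotes 8 and 9. For non-entrants, they call for a dose that Section 6.1.9 does not list.

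If a site gives an OLE entrant both doses, the excess over the scheduled 300 mg is 600 mg for a former active participant on full dose, 300 mg for one on the reduced dose, and nil for a former placebo participant. These sizes assume that the held dose is the one in force at Week 24 and that the site reads the sections as additive. How many sites would do so, and how many participants enter the OLE, cannot be determined from the documents.

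This is a contradiction in dosing text. No effect on the efficacy analyses or on the blinded adverse-event window is shown. It should be corrected because the passages disagree on what is given at a visit every completing participant is due to attend, and because aligning them costs almost nothing.

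**What to change.** Reconcile Protocol Sections 5.3.1, 8.2 and 6.1.9, footnote 14 of the placebo-controlled schedule, and OLE footnotes 8 and 9. Correcting Section 5.3.1 alone would leave the conflict in Section 8.2.

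- In both 5.3.1 and 8.2, take Week 24 out of the sentence shared with Weeks 4, 8 and 16 and give it its own sentence, cross-referenced to 6.1.9.
- State there, separately for OLE entrants and non-entrants, whether the held blinded dose is given after the trough sample.
- Make 6.1.9 and the three footnotes say the same, and check the Week 24 cell of the SAP schedule against them.
- In the same edit, align the timing: 5.3.1 and 8.2 place the dose within the visit, while 6.1.9 and footnote 18 place it after procedures.

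The sponsor decides which dosing rule applies; none is proposed here. The cost is a short text correction in the RSA and a site memo. Sample size, visit schedule and analyses are unaffected.
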